12.1 Clinical Criteria for Early Trial Termination

Early trial termination will be the result of the criteria specified below:

- Quality or quantity of data recording is inaccurate or incomplete
- Poor adherence to protocol and regulatory requirements
- Incidence or severity of adverse drug reaction in this or other studies indicates a potential health hazard to participants
- Plans to modify or discontinue the development of the study drug

In the event of Merck decision to no longer supply study drug, ample notification will be provided so that appropriate adjustments to participant treatment can be made.

13.0 CRITERIA FOR OUTCOME ASSESSMENT AND ENDPOINT EVALUABILITY

The two major effects to be measured in this study are: tumor/pathological response to study drugs and volumetric tumor assessment by MRI.

13.1 Target Lesions

A baseline and presurgical imaging study of the breast is required as necessary for clinical management; ultrasound, mammogram and MRI may be pursued. The baseline imaging must be obtained within 28 days (+/- 7 days) of beginning therapy. If the participant demonstrates clinical progression at any time, repeat imaging is required. If there is discordance (clinical progression, but radiographic stable disease or response), study PI should be contacted to solve discordance.

In the event of multifocal or multicentric disease in the breast, the investigator must determine which will represent the target lesion. This should remain consistent throughout the study. The target lesion should be selected on the basis of its size (lesion with the longest diameter) and suitability for accurate repetitive measurements (either by imaging techniques or clinically).

Response criteria are based on the RECIST 1.1 criteria:

Imaging Complete Response (CR):	Complete disappearance of the target lesion
Imaging Partial Response (PR):	Greater than or equal to 30% decrease in the longest diameter (LD) of the target lesion taking as reference the baseline LD
Imaging Progressive Disease (PD):	Greater than or equal to 20% increase in the LD of target lesion taking as reference the baseline LD or the appearance of one or more new lesions
Imaging Stable Disease (SD):	Neither sufficient shrinkage to qualify for PR nor sufficient increase to qualify for PD taking as reference the baseline LD

13.2 Pathological assessment

The MD Anderson Residual Cancer Burden (RCB) method will be used to assess pathologic response in the surgical specimen (Symmans et al. 2007; Provenzano et al. 2015). At least one complete cross-section of the largest dimension of tumor bed, and at least 1 section per centimeter of the tumor bed will be submitted for microscopic review. The entire tumor bed will be submitted if the largest diameter is less than 5 cm. The entire cross tumor bed section will be used to evaluate the following variables: tumor bed diameters (2 largest dimensions), tumor cellularity, percent of tumor cellularity that is DCIS, number of positive lymph nodes, and size of the largest nodal metastasis. If multiple tumors are present, the measurements of the largest will be used to calculate the RCB. If lymphovascular invasion is identified in the specimen in

the absence of residual invasive tumor or nodal involvement this will not be considered pCR.

RCB score will be calculated using the following online tool: <http://www3.mdanderson.org/app/medcalc/index.cfm?pagename=jsconvert3>. RCB 0/I will be considered good response; RCB II/III will be considered poor response. RCB0 is considered pCR. pCR will be defined as no residual invasive carcinoma and no lymph node metastasis regardless of the presence of DCIS.

13.3 Imaging assessment

Each participant will have a pre-therapy baseline MRI study. The longest diameter (LD) of the target lesion at the time of study initiation will be reported as the baseline LD. The baseline LD of the target lesion will be used as reference to further characterize the objective tumor response of the measurable dimension of the disease. There is no size requirement defining residual disease; the determination of the presence of clinically significant residual disease will be made by the treating provider. The radiologic response to treatment should be noted as complete response (no visible tumor present), partial response (tumor present but reduced in size from baseline), stable disease (no change in size of tumor) or progressive disease (tumor larger than baseline). Both target and, in the event of multifocal or multicentric invasive cancer, nontarget lesions should be followed clinically and their clinical size recorded at baseline. Measurements thereafter are required; these lesions should be categorized at subsequent visits regarding whether there is evidence of progression. If progression occurs the study chair should be notified in order to determine whether the participant should come off protocol treatment. In addition to measuring the longest diameter of the target lesion, quantitative volumetric assessment will be performed of the target lesion on all MRI using commercially available software **tararecon** (Foster City, CA).

13.4 Pathology Response Central Review

Central review of pathology slides of the baseline and on-study breast biopsies and the post-treatment surgical specimen (excision or mastectomy with lymph nodes) will be performed by [name] [name].

14.0 BIOSTATISTICS

This trial is designed as a single-arm, open-label, non-randomized study with sample size calculated using the Simon two-stage minimax design. The primary endpoint is pathologically negative MRI-guided biopsy after neoadjuvant combination olaparib-pembrolizumab therapy at 12 weeks. Patients are eligible for this study if they have newly diagnosed high-risk early-stage invasive breast cancer, either triple negative according to ASCO/CAP guidelines or hormone receptor positive breast cancer with a germline mutation in BRCA1, BRCA2, PALB2, RAD51C, or RAD51D. As noted in section 3.6, our preliminary work suggests that MRI-guided biopsy has high specificity

and sensitivity in diagnosing pCR compared with the reference of standard surgical pathology.

At the 6 week timepoint, patients will be categorized as follows:

Group 1: Decrease in tumor size

1a) Decrease in tumor size of at least 50% ($\geq 50\%D$)

1b) Decrease in tumor size at 6-weeks of 0 to 50% ($< 50\%D$)

Group 2: Enlargement in tumor size of 0 to 25% ($< 25\%E$)

Group 3: Enlargement in tumor size of 25% or greater

All evaluable patients across the 4 categories will be included for the primary endpoint.

Patients who are responding (any decrease in tumor size, groups 1a and 1b above) will continue the study therapy for another 6 weeks. Patients who have increases in tumor size of 0-25% (group 2) at the 6-week timepoint can continue study therapy for another 6 weeks or elect SoC chemotherapy/pembrolizumab vs surgery. To ensure safety, patients who have a $> 25\%$ increase in tumor size from the preceding imaging at any point (group 3) will immediately move to SoC chemotherapy vs surgery. For all 4 groups following completion of the study therapy, conventional treatment will commence. These group delineations are outlined in details because this determines how patients will be treated on study.

All patients who have received at least one dose of each study treatment will be assessable for safety of the combination therapy. Patients are evaluable for the primary endpoint if they have completed the 6-week assessment. Biopsy-confirmed radiographic complete response will be determined at the 12-week timepoint. pCR/RCB0 will be determined at the time of surgery.

Sample size

The primary endpoint is pathologic assessment of MRI biopsy after neoadjuvant combination olaparib-pembrolizumab therapy at 12 weeks. The primary efficacy endpoint will be evaluated following completion of neoadjuvant therapy with combination olaparib and pembrolizumab X 12 weeks. In the primary analysis, patients whose 12-week imaging assessment or biopsy is not available will be counted as failures in the primary endpoint.

Patients are evaluable for the primary efficacy analysis if they have completed the 6-week assessment. An exception to this includes the rare patients who progressed during the first 6 weeks. These patients will be included in the primary analyses as failures. Note that any patients with progression or who drop out of the study from week 6 to 12 will be counted as failures for primary 12 week endpoint. Also note that patients who require a switch to SOC chemotherapy/ pembrolizumab after the 6 weeks biopsy

will be considered failures for the primary endpoint. All patients are evaluable for the safety analyses.

All evaluable patients (groups 1-3) will be included in our primary analysis. The sample size for this study is calculated using a Simon two-stage minimax design comparing a null true imaging-based complete response rate of 50% vs 75%. Our null rate comes from published literature which reports pCR rates in the range of ~44-54% in patients receiving neoadjuvant cytotoxic chemotherapy and ~53-65% in patients receiving either neoadjuvant immunotherapy or a targeted agent like a PARPi^{59, 73, 74,75}. In the first stage, 14 patients will be accrued. If there are 7 or fewer responses, then the study will be stopped. If 8 or more responses are observed, an additional 9 patients will be accrued for a total of 23 patients. If 16 or more responses are observed in 23 patients, the study regimen will be deemed successful. If 15 or fewer responses are observed, the study will be deemed unsuccessful. This design has a one-sided type I error rate of 0.05 and power of 0.80. The probability of stopping the study under the null is 0.60. At the end of the study, the image-guided biopsy CR rate will be calculated with a 95% confidence interval.

Up to 23 evaluable patients will be enrolled on this study. We anticipate enrolling 1-2 patients per month.

Secondary endpoints

There are several secondary endpoints. First, safety and tolerability of the study regimen will be summarized using frequencies according to the CTCAE Version 5. Common side effects are listed in Section 15.0. The rate of pathologically negative MRI-guided biopsy at 12 weeks will be calculated in the subpopulation of patients with PD-L1-positive disease. In the neoadjuvant setting the rates of PD-L1 positivity were reported in two large prospective trials: Keynote 522 ~80% of patients with TNBC were PD-L1+ and in the NeoTrip trial ~56% of tumors were PD-L1+. In the metastatic setting the numbers have been varied but in the large clinical trials the rate of PD-L1 positivity was ~40%.

Data on MRI-guided biopsies and MRI images will be collected at baseline, at 6 weeks and at 12 weeks following entry into the study. The correlation of response as measured by the MRI - guided biopsy vs MRI images will be evaluated at each timepoint using the McNemar's test for paired samples. The correlation of response as measured by the MRI-guided biopsy collected post-treatment vs pCR at surgery will be evaluated using the McNemar's test for paired samples and the Kappa statistic. The overall pathologic complete response rate will be calculated with a 95% confidence interval.

Analysis of exploratory endpoints

These exploratory analyses will be descriptive/graphical in nature, and are designed to generate new hypotheses to be tested in future clinical studies.

When parameters of immune response are measured (including TILS, multiplex IH and cGAS-STING pathway expression) continuous variables will be summarized with means and standard deviations. Dichotomous and categorical variables will be summarized using proportions with exact 95% confidence intervals and counts, respectively. These summaries will be computed for each treated patient at multiple time points, including before treatment, during and after pembro/olaparib administration, as indicated in the study schema. Plots will be used to show the changes in immune response over time for each individual. For each patient, comparisons in the pre and post-treatment responses will be compared using paired t-tests (or Wilcoxon signed rank tests if appropriate) for continuous variables and McNemar's test for dichotomous or categorical variables. Associations between immune responses will be explored graphically (e.g. scatterplots, boxplots) and numerically (e.g. associations, χ^2 tests). Associations between early ctDNA values and pathologic response will be evaluated descriptively and graphically.

Bioinformatic and biostatistical analysis of differentially expanded/contracted clones in PBMC and tumor tissue after 6 and 12 weeks of treatment will be performed using Fisher's exact test with multiple testing correction by Benjamini-Hochberg procedure which controls false discovery rate (FDR < 0.05). Differential clonotypes will be further analyzed for tissue and longitudinal PBMC representation in pCR and non-pCR patients.

Analysis of the EPI-MRF and CEST-MRF: Maps from these sequences will be correlated with the histopathology measures. We will evaluate changes pre, 6-week and 12-week post neoadjuvant chemotherapy. We will compare these parameters between patients with a pathologic complete response versus those with no-pathologic complete response using two sample t-tests, or Wilcoxon rank sum tests if data are highly skewed. Once significant parameter changes are identified by these tests, we will then run ROC/AUC analyses to identify optimal cut-points by maximizing the Youden index (i.e., sensitivity + specificity - 1). Depending on specific requirements we may consider assigning various weights to sensitivity and specificity as well. Predictive power quantified by AUC can also be compared across different imaging parameters (e.g., T1-weighted, diffusion and DCE scans) and statistical significance level will be derived by, e.g., the Delong-Delong test to compare the predictive power of both EPI-MRF and CEST-MRF to the standard protocol. For time-to-event type endpoints, we will apply the Cox proportional hazards regression model (endpoints will be landmarked to ensure they are baseline factors in the Cox model) to identify significant factors and compute the concordance index for their predictive power. We will also try to identify optimal cut-points using the maximal chi-square method. Graphical presentation of the parameter measurements will be examined for patterns and appropriate longitudinal analysis tools may be used if such analyses are deemed necessary.

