4.2 Intervention

Patients will start both olaparib 300 mg PO BID and pembrolizumab 400 mg IV Q6W and continue BID dosing of olaparib with further infusions of pembrolizumab every 6 weeks. Patients will receive olaparib and pembrolizumab for 6-12 weeks, followed by SOC chemotherapy/pembrolizumab and surgery. The sequence of cytotoxic chemotherapy +/- pembrolizumab vs surgery after study treatment will be determined by the primary clinical team. Patients will undergo baseline and then 6-week volumetric radiographic tumor assessment with MRI. At the 6-week timepoint, all patients will undergo a biopsy at the time of radiographic tumor assessment with MRI. Radiographic

tumor assessment with MRI and biopsy will be repeated at 12 weeks (for those patients who remain on olaparib/pembrolizumab for > 6 weeks). The pre, 6-week and 12-week diagnostic MRI will incorporate the (1) EPI-MRF and (2) CEST-MRF sequences. The EPI-MRF sequence has been optimized for rapid measurements of quantitative susceptibility mapping, proton Density (PD), T1 and T2 relaxation maps. The sequence works by variable excitations and delays which simultaneously sensitizes the signal to the PD, T1 and T2 tissue parameters. Imaging time is approximately 6 seconds per slice with no intravenous contrast is needed. The CEST-MRF sequence is a multiparametric molecular imaging method for rapid simultaneous measurement of the water T1 and T2 relaxation maps, the pH-dependent amide exchange rate and volume fraction and the macromolecular exchange rate and volume fraction. The sequence is fast (acquisition time=2 minutes), requires no intravenous contrast. Both sequences are implemented on 3T GE scanners (Signa Premier). The acquisition time for both the EPI-MRF and CEST-MRF sequences together will take less than 10 minutes, which will ensure all MRI examination will be successfully completed within the allocated time slot.

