w: After informed consent has been obtained but prior to initiation of study treatment, only serious adverse events caused by a protocol -mandated intervention should be reported. After initiation of study treatment, all adverse events will be reported until 30 days after the last dose of study treatment.

x: All Patients will receive olaparib and pembrolizumab for 6-12 weeks, followed by SOC chemotherapy/pembrolizumab and surgery. Depending on response to study therapy at the post treatment wk 12 biopsy, the sequence of chemotherapy +/- pembrolizumab vs surgery will be determined by the primary clinical team. During SOC chemotherapy/pembrolizumab therapy, up to 2 visits are required to coincide with a CTN visit to assess toxicity and conmedication review and may be completed as telehealth visits.

y: The cycle length is based on pembrolizumab administration. Patients will be seen as per standard of care for assessments during chemotherapy.

z: Pembrolizumab may be administered within a +/- 2 week window depending on surgery scheduling.

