Grades 3 or 4 Grade 3: Prolonged (i.e., not rapidly responsive to symptomatic medication and/or brief interruption of infusion); recurrence of symptoms following initial improvement; hospitalization indicated for other clinical sequelae (e.g., renal impairment, pulmonary infiltrates) Grade 4: Life-threatening; pressor or ventilatory support indicated	Stop Infusion. Additional appropriate medical therapy may include but is not limited to: Epinephrine** IV fluids Antihistamines NSAIDs Acetaminophen Narcotics Oxygen Pressors Corticosteroids Increase monitoring of vital signs as medically indicated until the participant is deemed medically stable in the opinion of the investigator. Hospitalization may be indicated. **In cases of anaphylaxis, epinephrine should be used immediately. Participant is permanently discontinued from further study drug treatment.	No subsequent dosing
Appropriate resuscitation equipment should be available at the bedside and a physician readily available during the period of drug administration. For further information, please refer to the Common Terminology Criteria for Adverse Events v5.0 (CTCAE) at http://ctep.cancer.gov		

Other allowed dose interruptions for pembrolizumab

Pembrolizumab may be interrupted for situations other than treatment-related AEs such as medical / surgical events or logistical reasons not related to study therapy. Participants should be placed back on study therapy within 3 weeks of the scheduled interruption, unless otherwise discussed with the PI. The reason for interruption should be documented in the patient's study record.

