12.0 CRITERIA FOR REMOVAL FROM STUDY

Patients will be removed from the study when any of the criteria listed below applies. The reason for removal from the study and the date the patient was removed must be documented in the Clinical Research Database system.

All patients who have received at least one dose of each study treatment will be assessable for safety of the combination therapy. Patients who discontinue the study

before receiving their first dose of the study treatments will not be evaluable for safety assessment and should be replaced. Patients whose treatment is interrupted or permanently discontinued due to an AE or clinically significant laboratory value must be followed until resolution or stabilization of the event. A dose delay >3 weeks from the date of the planned dose may require the patient to be discontinued from the study treatment.

Patients are evaluable if they have completed the 6-week assessment. Radiographic response is assessed at 6 and (for those continuing) 12 weeks. Biopsy-confirmation of disease status at 6 and 12 weeks will be conducted at the time of the 6 and (for those continuing) 12 week assessments. pCR/RCB is assessed at the time of surgery.

Patient may continue on study until one of the following criteria applies:

- Confirmed radiographic disease progression
- Intercurrent illness that prevents further administration of treatment
- Unacceptable adverse experiences
- The participant or participant's legally acceptable representative requests to discontinue study treatment
- Physician decides to withdraw a participant from the study treatment or from the study for a reason not listed here
- The participant has a confirmed positive serum pregnancy test
- The participant is lost to follow-up
- Inability of the participant to comply with the requirement of the protocol for treatment or evaluation.
- End of study, whichever occurs first.

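### Sections 12 and 14 give conflicting safety sets, and the both-drugs version can leave out a patient who stops for toxicity after only one drug

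*Combined protocol and SAP*

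**What the plan says.** Four statements in the combined protocol and SAP bear on who is counted for safety.

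- Section 14.0, in the paragraph before Sample size: "All patients who have received at least one dose of each study treatment will be assessable for safety of the combination therapy". Section 12.0 carries the same rule.
- Section 14.0, Sample size, at the end of the paragraph on efficacy evaluability: "All patients are evaluable for the safety analyses".
- Section 12.0, on patients who leave the study "before receiving their first dose of the study treatments will not be evaluable for safety assessment and should be replaced".
- Section 14.0, Secondary endpoints: "safety and tolerability of the study regimen will be summarized using frequencies according to the CTCAE Version 5". No denominator is named.

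Three further provisions decide whether the difference can matter in practice.

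- Section 4.2: "Patients will start both olaparib 300 mg PO BID and pembrolizumab 400 mg IV Q6W". The order of first tablet and first infusion is not given.
- Section 11.2, infusion-reaction table, Grade 3 or 4: "Participant is permanently discontinued from further study drug treatment".
- Section 10.2, Study Calendar, footnote w: "After initiation of study treatment, all adverse events will be reported until 30 days after the last dose of study treatment".

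**The concern.** Safety and tolerability is the first secondary objective in Section 2.0. Two analysts could each follow the plan faithfully and report different rates, because one sentence requires exposure to both drugs and another imposes no exposure condition. Section 12.0 does not settle it: it deals with patients who leave before dosing and says nothing clear about a patient who received only one of the two drugs.

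The both-drugs rule is the more troublesome of the two. It makes membership of the safety set depend on something that happens after first exposure, namely whether the patient goes on to the second drug. If the first drug causes the toxicity that prevents this, the adverse event itself removes the patient from both numerator and denominator. The bias then runs in one direction, towards a lower reported toxicity rate. Such a patient may also be missing from the primary efficacy analysis, since Section 14.0 requires the 6-week assessment and makes an explicit exception only for early progression. An early toxicity dropout could then appear in neither table.

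**Working it through.** **1. The plan's own figures.** The documents give no figure for the safety set. The sample sizes come from the Simon two-stage design in Section 14.0: 14 patients, stop at 7 or fewer responses; then 23 in total, success at 16 or more; null rate 0.50, alternative 0.75. Exact binomial calculation gives a type I error of 0.0462 (stated 0.05), power of 0.8016 (stated 0.80) and a probability of early stopping under the null of 0.6047 (stated 0.60). The design reproduces. The safety set does not enter it, so nothing below alters it.

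**2. Who is in under each sentence.**

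| Patient | Both-drugs rule (12.0, 14.0) | All-patients rule (14.0, Sample size) | Pre-dose sentence (12.0) |
|---|---|---|---|
| Received both drugs | In | In | Not addressed |
| Received one drug only | Out | In | Not clearly addressed |
| Received neither | Out | In, read literally | Out, replaced |

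The middle row is the unresolved one.

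**3. When a first-infusion reaction leads to exclusion.** Two conditions must both hold: no olaparib was taken before the reaction, and none is given afterwards. Section 4.2 has both drugs starting together but does not give the order. The discontinuation rule sits in the pembrolizumab infusion-reaction table, where the study drug may mean pembrolizumab alone. Exclusion is possible but not certain. The mirror case is a patient who takes olaparib, has toxicity and never receives an infusion; the same gap applies.

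**4. Size if it happens once.** Assume one such patient among those treated. The rate is x/n, with exact (Clopper-Pearson) two-sided 95% intervals.

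- Full trial, counted: 1/23 = 4.3% (0.1% to 21.9%).
- Full trial, excluded: 0/22 = 0% (0% to 15.4%).
- Stage 1 stop, counted: 1/14 = 7.1% (0.2% to 33.9%).
- Stage 1 stop, excluded: 0/13 = 0% (0% to 24.7%).

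If the patient were also replaced, 24 would be treated and the comparison would be 1/24 = 4.2% against 0/23.

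**5. How often it could arise.** Section 15.0 puts pembrolizumab infusion reactions of any severity at 1 to under 5 per 100. The chance of at least one among 23 patients is 1 − (1 − q)^23. With q = 0.01 this is 20.6%; with q = 0.05 it is 69.3%. These are ceilings for the scenario in step 3, which also needs the reaction to be severe, to occur at the first infusion and to occur in a patient who never takes olaparib. The documents give no rate for that combination; it is lower by an unknown amount.

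**The case against.** The strongest reply is that the sentences can be read together. The both-drugs sentence concerns safety of the combination, and a patient who took one drug says little about a combination. The all-patients sentence closes a paragraph on efficacy evaluability, so it may only mean that failing the efficacy criteria does not remove anyone from safety. On that reading the plan has a broad safety set and a narrower combination set. This is reasonable, but the plan does not define two sets or say which supplies the CTCAE frequencies, so the ambiguity stands.

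The second reply is that the consequence is small. Adverse events are collected from the start of treatment whatever the analysis set, serious events are reported separately under Sections 15.1 and 15.2, and the institutional committee reviews the trial under Section 16.4. The safety analysis is descriptive, and Section 14.0 attaches no test, confidence bound or numerical stopping threshold to it. All of this is correct. What is at risk is the event's place in the reported table, not its detection, and the intervals in the working feed no planned decision.

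Three stronger readings are tempting and are not supported.

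- A reader might infer that the both-drugs rule necessarily drops anyone who stops after a severe first-infusion reaction. It does so only if olaparib is taken neither before nor after, and the documents settle neither point.
- A reader might infer that such a patient would be replaced. Section 12.0 replaces patients who leave before their first dose; someone who reacted to an infusion has had a dose of one study treatment, so replacement is only one possible reading.
- A reader might infer that the all-patients sentence dilutes rates with never-dosed patients. Section 12.0 says patients who leave before dosing "will not be evaluable for safety assessment and should be replaced", which largely answers this.

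**Conclusion.** The inconsistency is real and rests on wording alone: the two safety sets conflict whatever the dosing order, one-drug patients have no settled status, and no denominator is named. The possible harm is that toxicity after one drug takes a patient out of the safety table. That depends on at least one patient stopping for toxicity without ever receiving the second drug, and on the analyst applying the both-drugs rule.

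The size is one patient's worth of rate for each such case, about 4 percentage points at full enrolment and 7 at stage 1, with the observed event disappearing from the table. Few patients are likely to be affected. This is a minor point of definition, worth correcting because the ambiguity is avoidable and the possible bias favours the regimen.

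**What to change.** In Sections 12.0 and 14.0:

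- Define one safety set as all patients who received any dose of olaparib or pembrolizumab, and remove the competing sentences.
- Name that set as the denominator for the CTCAE frequencies under Secondary endpoints.
- State that only patients who received neither drug are non-evaluable for safety and are replaced on that ground.
- If a both-drugs set is wanted to describe the combination, keep it and label it supplementary.

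The cost is a few sentences. No treatment rule, data collection, sample size, type I error or power changes. The edit should be made before any safety data are tabulated, so that the denominator is not chosen with the events in view.
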